10. CLINICAL MONITORING

10.1. Site Monitoring Plan

Site monitoring is conducted to ensure that the human subjects' protections, study and laboratory procedures, study intervention administration, and data collection processes are of high quality and meet sponsor, ICH/GCP guidelines, and applicable regulations, and that this trial is conducted in accordance with the protocol, protocol-specific MOP, and applicable sponsor standard operating procedures. DMID, the sponsoring agency, or its designee will conduct site-monitoring visits as detailed in the clinical monitoring plan.

Site visits will be made at standard intervals as defined by DMID and may be made more frequently as directed by DMID. Monitoring visits will include, but are not limited to, review of regulatory files, accountability records, eCRFs, informed consent forms, medical and laboratory reports, and protocol and GCP compliance. Site monitors will have access to each participating VTEU site, study personnel, and all study documentation according to the DMID-approved site monitoring plan. Study monitors will meet with site principal investigators to discuss any problems and actions to be taken and document visit findings and discussions.

11. STATISTICAL CONSIDERATIONS

The primary goals of this study are to assess the safety and tolerability of BOOSTRIX when administered to pregnant women, as well as to determine the maternal and infant immune response. Additional goals include evaluating the effect of maternal antibody on primary infant immune responses to DTwP, identifying cofactors associated with infant and maternal immune responses and determining immune responses in colostrum/breast milk.

11.1. Study Hypotheses

BOOSTRIX will be safe and well tolerated in pregnant women and will lead to PT levels that are higher in the pregnant women and their infants as compared to pregnant women vaccinated with a Td vaccine and their infants. This is one of the first studies of maternal Tdap vaccination in a low resource setting in Africa, and where infants received whole cell, rather than acellular pertussis vaccinations. Thus, this study is intended to obtain preliminary estimates of immune response in this setting; it is not designed to test a formal hypothesis.

11.2. Sample Size Considerations

11.2.1. Study Design

This is a phase II, randomized, double-blind, active-controlled study in which 200 healthy pregnant women, ages 18 through 39 years, inclusive, will be randomly allocated in a 2:1 ratio to receive either Tdap (BOOSTRIX) or Td at 14 0/7 weeks through 26 6/7 weeks estimated GA. After signing an ICF, all subjects will undergo a review of current and past medical history, current and prior medication use, and recent and relevant vaccination history. All pregnant subjects will have a physical examination as part of routine antenatal care. For the fetuses of pregnant subjects, GA will be established by ultrasound, whenever possible, in combination with date of LMP, when available, and fundal height. Subjects will be enrolled, vaccinated, and followed for safety, tolerability, and immune responses as described in this protocol.

11.2.2. Study Population

200 healthy pregnant women, ages 18 through 39 years, inclusive, who meet all eligibility criteria, and their infants.

Based on the accrual rate for similar studies, it seems reasonable to expect that the sites will be able to enroll this study in a timely fashion. Prior experience suggests up to 15% of subjects may be excluded from the per protocol analysis for the primary immunogenicity outcome either because they were lost-to-follow-up or otherwise do not have data available following the study vaccination, or because they had a protocol deviation requiring their exclusion from the per protocol analysis.

11.2.3. Sample Size

The study is planned to enroll 200 pregnant women (133 BOOSTRIX, 67 Td).

This will be one of the first studies of maternal Tdap vaccination in an African, low resource setting, and where infants received whole cell, rather than acellular pertussis vaccinations. Thus, this study is intended to obtain preliminary estimates of immune response in this setting; it is not designed to test a specific null hypothesis. The tables below describe the power to detect safety events and the precision available for estimating immune response for the planned sample size. [Table 9](#) indicates the probability of observing one or more safety event, such as solicited injection site or systemic symptom, or an unsolicited adverse event of a particular type within a treatment arm.

Table 9: Power (%) to Detect Safety Events

Event Frequency	N = 133	N = 67
≥0.01% Rare	1.3	<1
≥0.1% Uncommon	12.5	6.5
≥1% Common	73.7	49.0
≥10% Very Common	100.0	99.9

In addition to safety, as a co-primary objective, the study will assess serum PT antibody at birth among infants whose mothers received a single dose of BOOSTRIX, and as secondary and exploratory objectives, the study will assess maternal and infant humoral response to all vaccine antigens. Immune response will be measured by ELISA. [Table 10](#) presents the precision (95% CI) available for estimating GMC of ELISA titers against the vaccine component using assumptions for GMC and standard deviation (SD) for maternal and infant response to Tdap from Munoz et al. [13] and infant response post third dose of primary DTwP vaccine series from Ladhani et al. [34]

Table 10: Precision for Estimating GMC of ELISA Antibody Response

GMC	SD (log-scale)	95% CI Estimate		
		N = 133	N=67	
Maternal ELISA Antibodies at Delivery following maternal Tdap				
PT	51	0.90	43.7	59.5
FHA	184.8	0.73	163.1	209.3
PRN	184.5	1.45	143.8	236.7
FIM	1485.7	1.17	1214.8	1817.0
Infant ELISA Antibodies at Birth following maternal Tdap				
PT	68.8	0.78	60.2	78.7
FHA	234.2	0.67	208.7	262.8
PRN	219	1.38	172.9	277.4
FIM	1867	1.22	1514.7	2301.3
Infant Response post 3rd Dose DTwP following maternal Tdap				
PT	28.8	0.68	25.6	32.3
FHA	25.5	0.60	23.0	28.3
FIM	113.9	0.81	99.1	130.9
Infant Response post 3rd Dose DTwP (no maternal vaccination)				
PT	43.2	0.65	38.6	48.3
FHA	41.1	0.66	36.7	46.1
FIM	224.9	0.97	190.2	265.9
			177.2	285.4

Table 11 presents the minimum difference in infant PT antibody GMC at birth between the Td and Tdap (BOOSTRIX) vaccination arms that would be detectable with 80% power. The assumed GMC and SD used for these calculations are based on the PT antibody GMC and SD observed at birth in infants whose mother received either Tdap or placebo vaccination during pregnancy, reported in Munoz et al. [13]. The calculations are based on a two-sided two sample T-test to compare means, with alpha = 0.05.

**Table 11: Minimum Detectable Difference in Infant PT Antibody GMC at Birth
Comparing Infants Born to Mothers Vaccinated with BOOSTRIX versus Td**

Td	Tdap (BOOSTRIX)	Assumed GMC (BOOSTRIX)	Maximum GMC Detectable with Power = 0.8 (Td)	Minimum Detectable Difference (BOOSTRIX - Td)
N=67	N=133	50.0	33.1	16.9
		60.0	40.4	19.6
		70.0	44.7	25.3
		80.0	49.4	30.6
		90.0	60.3	29.7

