5.3.5. Subject Replacement

Subjects who sign the informed consent form and are randomized but do not receive study vaccine may be replaced. Subjects who sign the informed consent form and are randomized and vaccinated, and subsequently withdraw or are withdrawn or terminated from this study or are lost to follow-up, will not be replaced. The proposed sample size for the trial accounts for a 15% rate of subject loss.

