11.4.3. Immunogenicity Data (ELISA)

Immunogenicity data summaries and analysis for pregnant women will be presented for the ITT and the PP populations. Immunogenicity data summaries and analysis for infants will be presented for the infant ITT and infant PP populations.

Immune responses will be reported for antibodies against each of the antigens in the vaccine and at each time point for each subject group- pregnant women receiving BOOSTRIX, pregnant women receiving Td, and the infants of women who received BOOSTRIX or Td while pregnant. GMC and corresponding 95% confidence intervals will be reported.

For each antigen, GMC will be compared between treatment arms using a t-test on log-transformed ELISA titers.

The level of antibody transplacentally transferred will be summarized as the Geometric Mean Ratio (GMR), with corresponding 95% confidence interval, of mother's concentration to infant's concentration for all mother-infant pairs for which both the mother and infant have data at the applicable time point (delivery/birth).

Graphical presentations of immune response may include reverse cumulative distribution (RCD) curves, and longitudinal presentations of GMTs.

To evaluate the association with of maternal immunogenicity cofactors, Maternal and Infant anti-PT ELISA response will be summarized stratified by maternal age (18-29, 30-39 years old), parity (primiparous vs. multiparous), GA at time of vaccination (14-17, 18-21, 22-26 weeks), GA at time of delivery (28-32, 33-36, 37 or more weeks), and infant birthweight, and these cofactors will be evaluated in regression modeling.

Antibody responses in breast milk/colostrum will be evaluated in a similar way to above.

Additional exploratory analyses, including analysis of cytokine response will be described in the statistical analysis plan.

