## 5. SAMPLE SIZE CONSIDERATIONS

Based on the accrual rate for similar studies, it seems reasonable to expect that the sites will be able to enroll this study in a timely fashion. Prior experience suggests up to 15% of subjects may be excluded from the per protocol analysis for the primary immunogenicity outcome either because they were lost-to-follow-up or otherwise do not have data available following the study vaccination, or because they had a protocol deviation requiring their exclusion from the per protocol analysis.

The study is planned to enroll 200 pregnant women (133 BOOSTRIX, 67 Td) and their infants.

This will be one of the first studies of maternal Tdap vaccination in an African, low resource setting, and where infants received whole cell, rather than acellular pertussis vaccinations. Thus, this study is intended to obtain preliminary estimates of immune response in this setting; it is not designed to test a specific null hypothesis.

**Table 3** indicates the probability of observing one or more safety event, such as solicited injection site or systemic symptom, or an unsolicited adverse event of a particular type within a treatment arm.

In addition to safety, as a co-primary objective, the study will assess serum PT antibody at birth among infants whose mothers received a single dose of BOOSTRIX or Td, and as secondary and exploratory objectives, the study will assess maternal and infant humoral response to all vaccine antigens. Immune response will be measured by ELISA. **Table 4** presents the precision (95% confidence interval (CI)) available for estimating GMC of ELISA titers against the vaccine component using assumptions for GMC and standard deviation (SD) for maternal and infant response to Tdap from Munoz et al. [10] and infant response post third dose of primary DTwP vaccine series from Ladhani et al. [11]

**Table 5** presents the minimum difference in infant PT antibody GMC at birth between the Td and Tdap (BOOSTRIX) vaccination arms that would be detectable with 80% power. The assumed GMC and SD used for these calculations are based on the PT antibody GMC and SD observed at birth in infants whose mother received either Tdap or placebo vaccination during pregnancy, reported in Munoz et al. [10] The calculations are based on a two-sided two sample T-test to compare means, with alpha = 0.05.

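### The 80%-power table for infant PT at birth (Protocol Table 11, SAP Table 5) does not follow from its stated t-test, omits the control-arm SD, and has no row net of the 15% loss

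*Protocol*

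**What the plan says.** Protocol 11.2.3 describes the content of Table 11 as follows: "minimum difference in infant PT antibody GMC at birth between the Td and Tdap (BOOSTRIX) vaccination arms that would be detectable with 80% power". Sample sizes are 133 BOOSTRIX and 67 Td. The GMC and SD inputs are attributed to a published trial, as values "observed at birth in infants whose mother received either Tdap or placebo vaccination during pregnancy". SAP section 5 repeats the method: "The calculations are based on a two-sided two sample T-test to compare means, with alpha = 0.05". The table itself reappears unchanged as SAP Table 5. The analysis it supports is set out in Protocol 11.4.3: "GMC will be compared between treatment arms using a t-test on log-transformed ELISA titers".

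The only log-scale SD printed for infant PT at birth is 0.78, in the Table 10 block headed "Infant ELISA Antibodies at Birth following maternal Tdap". No value is given for infants of control mothers. The 0.65 that Table 10 shows for PT without maternal vaccination is measured after the third DTwP dose, not at birth.

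On loss, Protocol 5.3.5 states: "The proposed sample size for the trial accounts for a 15% rate of subject loss". Protocol 11.2.2 adds: "Prior experience suggests up to 15% of subjects may be excluded from the per protocol analysis for the primary immunogenicity outcome". Tables 10 and 11 are calculated only at 133 and 67.

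**The concern.** If sample sizes, alpha, power and log-scale SDs are fixed, the smallest detectable effect on the log scale is a single number, which is a fixed ratio of GMCs. Multiplying a fixed ratio by a larger assumed GMC must give a larger absolute difference. Table 11 breaks this between its last two rows.

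This is the only between-arm power statement for the co-primary immunogenicity endpoint, and it stands in both documents. Without the control-arm SD, a reader cannot tell whether the printed differences are conservative or optimistic. The loss sentence raises a related traceability problem, because it claims an allowance that no immunogenicity calculation shows.

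**Working it through.** **Inputs.** Two-sided alpha 0.05, 80% power, 133 and 67 infants (Protocol 11.2.3); natural-log analysis (Protocol 11.4.3); BOOSTRIX-arm log SD 0.78 (Table 10); loss 15% (Protocol 5.3.5). The Td-arm SD is not in the documents, so it is treated as an assumption over a range.

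**Check that 0.78 is being read correctly.** Table 10, infant PT, N=133: 68.8 × exp(±1.978 × 0.78/√133) = 68.8 × exp(±0.1338) = 60.2 to 78.6. The printed interval is 60.2 to 78.7, so 0.78 is a natural-log SD and Table 10 reproduces.

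**What Table 11 should look like.** With a common SD, the detectable log difference is about (1.960 + 0.842) × SD × √(1/133 + 1/67) = 2.802 × 0.78 × 0.1498 = 0.327; the exact noncentral-t value is 0.329. The detectable ratio is exp(−0.329) = 0.720 in every row, and the differences would be 14.0, 16.8, 19.6, 22.4 and 25.2.

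**What is printed.** The last two columns give the SD each row would need for 80% power at 133/67. The Td SD column holds the BOOSTRIX SD at 0.78 and uses Welch degrees of freedom.

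| BOOSTRIX GMC | Td GMC | Difference | Ratio | Ratio range allowed by rounding | Implied common SD | Implied Td SD |
|---|---|---|---|---|---|---|
| 50 | 33.1 | 16.9 | 0.662 | 0.6610–0.6630 | 0.978 | 1.058 |
| 60 | 40.4 | 19.6 | 0.673 | 0.6725–0.6742 | 0.938 | 1.002 |
| 70 | 44.7 | 25.3 | 0.639 | 0.6379–0.6393 | 1.063 | 1.173 |
| 80 | 49.4 | 30.6 | 0.618 | 0.6169–0.6181 | 1.143 | 1.279 |
| 90 | 60.3 | 29.7 | 0.670 | 0.6694–0.6706 | 0.950 | 1.019 |

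Each subtraction is correct, so the irregularity lies in the Td column or in undisclosed inputs. The rounding ranges (Td value ± 0.05, divided by the BOOSTRIX GMC) do not overlap, so rounding is not the cause.

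**Other readings.** A t-test on untransformed values with a fixed SD gives the same difference in every row. A constant coefficient of variation gives a constant ratio again. Changing the sample size, sidedness or power moves the level of the table but not its pattern. Only SDs that differ from row to row could produce these figures, and neither document describes any.

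**Effect of the missing SD and of loss.** Net of 15%: 0.85 × 133 = 113 and 0.85 × 67 = 57. The BOOSTRIX SD is held at 0.78. Pooled degrees of freedom are used for equal SDs and Welch for unequal.

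| Assumed Td SD | Detectable ratio, 133/67 | 113/57 | Difference at GMC 70 (printed 25.3), 133/67 | 113/57 | Power at the five printed differences, 133/67 | 113/57 |
|---|---|---|---|---|---|---|
| 0.78 | 0.72 | 0.70 | 19.6 | 21.0 | 92–98% | 87–97% |
| 0.90 | 0.69 | 0.67 | 21.4 | 22.9 | 86–96% | 80–93% |
| 1.0 | 0.67 | 0.65 | 22.8 | 24.4 | 80–93% | 73–88% |
| 1.2 | 0.63 | 0.61 | 25.7 | 27.4 | 68–84% | 61–78% |

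If instead each row's implied common SD were the true one, power at 113/57 would be 73% in every row. Loss hardly affects precision: at N=113 the infant PT interval is 68.8 × exp(±1.981 × 0.78/√113) = 59.5 to 79.6.

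**The case against.** The strongest reply is that the table carries little weight. The protocol describes the study as estimating immune responses rather than testing a hypothesis, no passage derives 200 from Table 11, and the precision figures in Table 10 hold up. That limits how serious the point is. It does not excuse an 80%-power claim that is internally inconsistent, for a comparison the SAP will report with a p-value.

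Second, the text names its source trial and never says that one SD pair served all five rows. Citing a source for an input is ordinary practice, and row-specific SDs could generate these numbers. Strictly, then, the table is not reproducible from anything disclosed. But the text describes one source and no variation by row, and a reader needs the control SD to verify or correct the result.

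Third, the PT log SDs printed in Table 10 lie between 0.65 and 0.90. For a Td SD of 0.78 to 0.90, the printed differences keep about 80% power or more even at 113/57. That stands: the figures clearly below 80% need a Td SD above any PT value the documents print, so they are not evidence of a likely shortfall.

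Fourth, on loss, the protocol says its tables show "the precision available for estimating immune response for the planned sample size", so using 133/67 is disclosed, and the 15% sentence could mean only that 200 leaves some room. Even so, the sentence says the size accounts for loss, and no calculation does that.

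**Conclusion.** The point holds and should be fixed. No single common SD fits the five rows (implied values 0.94 to 1.14). With the BOOSTRIX SD at the printed 0.78, no single Td SD fits either (implied values 1.00 to 1.28). The fall from 30.6 to 29.7 is the plainest sign of this, and the GMC 70 and 80 rows are both out of line with the other three. These statements rest only on printed figures and the stated test.

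The power ranges rest on an assumed Td SD and show only that the table's meaning depends on an unstated input. The 15% sentence has no visible calculation behind it. Nothing here shows that the trial is too small, and the planned analysis is unaffected. Table 9 (safety events) is not in question.

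**What to change.** Recalculate Protocol Table 11 and SAP Table 5. State the log-scale SD used in each arm, that the test is on the log scale, and whether it assumes equal variances. Report the detectable GMC ratio, with absolute differences alongside if wanted, at 133/67 and at about 113/57. The ratios shown here illustrate assumed SDs and should not be copied in; the actual control-arm SD is needed. Then either let the 113/57 row support the 15% sentence in Protocol 5.3.5 or delete that sentence.

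The cost is one recalculation, table edits in two documents and one sentence in the protocol, with no change to enrolment, conduct or analysis.

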11.3. Planned Interim Analyses

Interim analyses would only be used to terminate this trial in the event that unanticipated safety events deemed to be of sufficient concern to require such action by the sponsor. A DSMB will be convened by DMID to review study progress and subject, clinical, safety, and reactogenicity data.

Cumulative safety information, study status, and primary endpoint results may be presented at a public forum in a blinded manner or presented as summaries aggregated by study arm at the discretion of the sponsor while the primary study is ongoing. While the primary study is ongoing no data will be released that is unblinding at an individual subject level, and caution will be taken to ensure that data summarized by treatment arm does not identify the treatment assignment of any individual subject. Any ad-hoc analyses, jointly developed by the SDCC and/or University of Maryland, will be executed by the SDCC as needed.

None of the interim analyses will include any formal statistical hypothesis testing; therefore, p-value adjustment will not be made to any analyses.

11.3.1. Interim Safety Review

An interim safety review will occur when safety data collected through Day 8 is available for 25% of pregnant study subjects. Reports for interim safety reviews will include data for pregnant participants, and any infants born at the time of data cutoff. Summaries may include enrollment and demographic information, medical history, concomitant medications, physical assessments, and solicited and unsolicited AE/SAEs. Additional data may be requested by the DSMB as described in [Section 9.6.2](#).

This trial will be monitored to determine if any of the halting rules described in [Section 9.5](#) are met.

11.3.2. Interim Immunogenicity or Efficacy Review

An interim immunogenicity review is not planned.

11.4. Final Analysis Plan

A formal statistical analysis plan will be developed and finalized prior to database lock.

11.4.1. Analysis Populations

The Safety Analysis population includes all pregnant women who received the study vaccination, and all infants born during the study.

The maternal intent-to-treat (ITT) population for immunogenicity analyses includes all pregnant women who received the study vaccination.

The maternal per-protocol (PP) population for immunogenicity analyses includes all subjects in the ITT subset with the following exclusions:

- Data from all available visits for subjects:
 - Found to be ineligible at baseline.
 - Without results from the baseline visits.
 - Without results from at least one post-vaccination visit.
- Data from all visits subsequent to major protocol deviations, such as:
 - Receipt of non-study licensed vaccine within the pre-specified exclusion windows ([Section 5.2](#)).
 - Receipt of immunosuppressive therapy (e.g., corticosteroids) within 30 days prior to or after study vaccination.
- Data from any visit that occurs substantially out of window.

The infant ITT population for immunogenicity analyses includes all infants born to women who received the study vaccination.

The infant PP population for *primary and secondary* immunogenicity analyses includes all infants in the ITT subset who have a blood sample from the perinatal period (cord blood or drawn blood within the 72 hours after birth).

The infant PP population for *exploratory* immunogenicity analyses includes all infants in the ITT subset with the following exclusions:

- Infants who did not receive DTwP within appropriate window.
- Infants who received any product that would impact immune response.
- Infants with blood samples captured substantially out of window.

In the case of mis-randomization, subjects will be analyzed according to the study product actually received for all analysis populations.

11.4.2. Safety Data

Maternal safety and tolerability, and fetal/infant outcomes will be summarized for the Safety Analysis Population.

Solicited AEs will be summarized by severity on days 4 and 8 after the study vaccination and as the maximum severity over the 8 days. Additionally, solicited AEs will be analyzed by taking the most severe response over the follow-up period, dichotomizing into a binary variable (none versus mild, moderate, or severe) and using standard techniques, such as exact confidence intervals, to summarize the proportion of subjects reporting each symptom, any injection site symptom, and any systemic symptom.

Unsolicited AEs will be coded by Medical Dictionary for Regulatory Activities (MedDRA®) for preferred term and system organ class (SOC). The number of SAEs is expected to be small in this trial, so these events will be reported by detailed listings showing the event description, MedDRA® preferred term and SOC, date of study vaccination, event date, severity, relatedness, and outcome for each event. Non-serious unsolicited AEs will be summarized as number and percentage of subjects reporting at least one event in each MedDRA® preferred term and SOC, tabulated by severity and relationship to study product. Additionally, the proportion of subjects and exact 95% confidence intervals of AEs in aggregate and by MedDRA® categories will be computed.

The proportion of subjects reporting solicited or unsolicited AEs may be compared between treatment arms using Fisher's exact test. The number of untoward fetal outcomes, perinatal complications, and major congenital abnormalities is expected to be small and so these events will be reported by a detailed listing including the event description, MedDRA® preferred term and SOC, relevant dates (study vaccination and AEs), severity, relatedness, and outcome for each event. If more than 5% of pregnant women experience untoward fetal outcomes, perinatal complications, or infants born with major congenital abnormalities, the proportion of subjects with such events will be compared between the BOOSTRIX and Td treatment arms using Fisher's Exact test.

